This protocol summarises plans for a pilot randomised controlled trial (RCT) and process and implementation evaluation of a pilot to embed systemic practice in keyworker teams as part of the Department for Education's Supporting Families Programme. The aims of the pilot trial are to:

1. Provide indicative evidence of the impact and efficacy that the model delivers on family outcomes compared to models that have not embedded systemic practice in their keyworker teams, and;
2. Establish the feasibility of delivering a full trial of the model in a larger number of local authorities.

A consortium led by Coram and the Institute of Family Therapy (IFT) will deliver the pilot. Twelve local authorities submitted Expressions of Interest (EOIs) and entered the randomisation process, six were randomised into the intervention group and six into the control group. Unfortunately, two local authorities in the control group dropped out of the pilot due to capacity and internal transformation projects taking place. The pilot RCT therefore comprises ten local authorities, six in the intervention group and four in the control group.

The pilot began in October 2024 and will end in May 2026. The evaluation is being led by Coram, partnering with Ecorys.

The six intervention group local authorities have begun embedding of systemic practice. This has included training in systemic practice to keyworkers by IFT, the hiring of systemic practitioner by local authorities and on-going support via a virtual systemic practice hub run by IFT and IFT's Systemic Psychotherapist Delivery Lead. The four control group local authorities not embedding systemic practice in the pilot period are being provided with technical support to collect data throughout the pilot and will receive training in systemic practice at the end of the trial period.

Findings will inform the development of the Families First Partnership programme delivery and wider children's social care policy, including the Government's reform of children's social care.

Background and previous evidence

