| Secondary outcome(s) | 
Variable(s):
 
 1. Family functioning 2. Therapeutic alliance 3. Step-up to children's social care 4. Positive progress made by families 5. Professional wellbeing 6. Quality of practice 
Measure(s) (instrument, scale, source):
 
 1. SCORE-15 Index of Family Functioning and Change 2. The Consultation and Relational Empathy (CARE) measure 3. Outcome at closure – Early Help dataset 4. Outcome at closure – Early Help dataset 5. An adapted measure of professional wellbeing 6. An adapted measure of systemic practice quality |
| Baseline for primary outcome | 
Variable: Progress towards personal goals
 
Measure(s) (instrument, scale, source): Goal Based Outcomes (GBO)
 |
| Baseline for secondary outcome | 
Variable(s):
 
 1. Family functioning 2. Therapeutic alliance 3. [None] 4. [None] 5. Professional wellbeing 6. Quality of practice 
Measure(s) (instrument, scale, source):
 
 1. SCORE-15 Index of Family Functioning and Change 2. The Consultation and Relational Empathy (CARE) measure 3. [None] 4. [None] 5. An adapted measure of professional wellbeing 6. An adapted measure of systemic practice quality |

Randomisation and blinding

The unit of randomisation is at the local authority level. We have randomised at a local authority level for two main reasons:

- Contagion effects at a keyworker, or family level. The practice model is a whole service approach which would be difficult to implement if randomisation took place either at a team, keyworker, or family level. This was a key concern in Foundation's Rotherham pilot study which could have contributed to its limited effects.⁵²
- Ethical considerations. Having received initial advice from Coram's Research Ethics Committee, ethical issues were identified in a trial that provided psychologically informed keyworker practice to some families and not others within the same service as the support families would receive could be very different. There may also be a tendency to prioritise families receiving support from systemically trained keyworkers.

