- The arm being allocated with the County Council serving more families (compared to the other County Council) was allocated the Metropolitan Council serving fewer families (compared to the other Metropolitan Council), and the trial arm with the County Council serving fewer families was allocated the Metropolitan Council serving more families compared to the other Metropolitan Council.
- The arm being allocated with the County Council serving more families was allocated the London Borough serving most families, as well as the Unitary authority serving the least families. The other two London boroughs were allocated to the other trial arm.
- The remaining Unitary authorities were allocated randomly across trial arms.

While this process was not completely random, it did guarantee a more equitable split of the sample across the two trial arms. For comparison, we simulated three processes completely at random, to see how the allocations vary across trial arms. To test the performance of the approaches, 100 simulations of each randomisation were conducted to compare the variation of the gap between arm allocations. As was expected, the more deterministic approaches have a smaller gap in the number of families between trial arms, while the more random approaches have bigger gaps. While the minimum gaps are smaller in the more random approaches, they occur with very low probabilities (~ 5%), with the overall approach having a larger variation.

The approach set out above was used to ensure an equitable distribution of families. This approach also ensured a more equitable distribution of the keyworker sample across arms. To strengthen the validity of the approach further, baseline equivalence testing⁵³ of possible allocations across trial arms was carried out against relevant covariates⁵⁴ to examine any possible bias emerging within trial arms. There was no significant difference between the covariates across the two arms in any of the scenarios (alpha = 0.05).

In addition, those undertaking the trial analysis will be blinded to randomisation. We will prepare the main analytical dataset so that trial arm is indicated by numbers and there is no data about participation in the pilot trial (i.e. the data analyst cannot infer which

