Recruitment of families into the pilot study has the advantage of being determined by eligibility for support by keyworkers. As a result, all families supported by a keyworker within the trial period will be eligible to be included within the trial if they consent to take part when completing the Family Outcome Questionnaire. Keyworkers in both control and intervention local authorities will receive training and detailed guidance in administering the Family Outcome Questionnaire. They will also receive ongoing support from Coram as well as from their local authority systemic practitioner including refresher training and drop-in sessions for troubleshooting.

Sample size calculations

When using a mixture of initial and revised numbers of families supported by local authorities that expressed an interest in the pilot, we decided to consider only 75% of the reported figures in our calculations. Our reasoning behind this was that whilst local

authorities provided their caseloads, we want to be cautious when taking these numbers into our estimates, as the caseload numbers may contain errors or old data, may include inactive or ineligible cases, and may include cases that are inaccessible as part of an evaluation owing to practicalities such as families relocating.

We hence conservatively estimate that the systemic practice trained keyworkers would potentially be dealing with 7,766 families, of which 1,165 families would participate in our programme data collection at baseline. Based on our assumptions on trial attrition in the CONSORT, this would amount to an analysable sample of 560 families, which was used to estimate an MDES of 0.446. While the dropout has led to a potential imbalance between treatment and control (65%:35%), this has been accounted for in our power calculations. We feel that this MDES is sufficient to detect a significant change using the GBO, with studies showing effect sizes^{55,56,57,58,59}

Table 2: Sample size calculations

| Parameter | Value |
|---------------------------------------|--|
| Minimum Detectable Effect Size (MDES) | 0.446 |
| Pre-test/ post-test correlations | Level 1 (participant): 0.6 Level 2 (family): 0.6 Level 3 (LA): 0.6 |
| Intraclass correlations (ICCs) | Level 2 (family): 0.3 Level 3 (LA): 0.1 |
| Alpha | 0.05 |

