| Number of families ⁶⁰ | Intervention: 361 Control: 199 Total: 560 |
| Number of participants | Intervention: 369 adults, 193 children Control: 203 adults, 101 children Total: 572 adults, 294 children |

⁶⁰ Final numbers reported (post attrition) that we will be analysing, rather than in the entire sample.

Updated sampling calculation (LAs = 10) – Only SF sample and latest assumptions

[figure not shown]

Figure 3 – Sampling calculations

SF Sample Size Calculation Table

| | |
|--------------------------------|------------|
| MDES | 0.446 |
| Alpha Level (α) | 0.05 |
| Two-tailed or One-tailed Test? | Two-tailed |
| Power (1- β) | 0.8 |
| Baseline/Endline correlations | |
| Individuals | 0.6 |
| Families | 0.6 |
| Local authorities | 0.6 |
| Average cluster size | |
| Individuals in families | 1.5 |
| Families in local authorities | 56 |
| Number of local authorities | 10 |
| Intraclass cluster correlation | |
| Families | 0.3 |
| Local authorities | 0.1 |

Assumptions

- 3 level clustering – individual in family in local authority
- Assumed a low ICC for families in terms of family functioning (expect different views)
- Assumed a very low ICC for local authorities in terms of family functioning (some clustering of scores based on shared factors, but not strong)
- Assumed baseline/endline correlations of 0.6 at all levels (unknown)

Figure 4 – SF Sample size calculation table

Outcome measures

Table 3: Primary outcome measures

| Variable | Progress towards personal goals |
|------------|--|
| Measure | Goal Based Outcomes (GBO) ⁶¹ |
| Sample | Parents/carers and children/young people aged 8 and over. The GBO will be administered as part of the Family Outcome Questionnaire at an individual level by keyworkers. There will be an adult version (for use with adults and young people aged over 12) and a child-friendly version (for use with children aged 8 to 12). Total GBO scores will be reported, as well as themed scores. We anticipate theming goals using existing taxonomies from psychotherapy research ^{62,63} and using inductive analysis owing to the novel context for use of the GBO. |
| Time point | Baseline: within the assessment period of the first six weeks of the keyworker working with a family. Midline: at a review point when working with the family. Typically, this is between two to five months of working with the family. Endline: At closure when the keyworker stops working with a family. |

Secondary outcome measures for families:

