- 2) *missing at random* (data is not randomly distributed but they are accounted for by other observed variables), or
- 3) *missing not at random* (data systematically differs from the observed values) and adjust our approach to analysis based on this assessment.

Where data is missing completely at random, no imputation will be carried out and only available cases will be analysed. Where data is missing at random it will be considered whether multiple imputation is required. Where data is missing not at random it will be considered which sensitivity analyses are required to produce estimates that adjust for missingness.

We anticipate all variables will be analysed using a three-level multilevel modelling approach for family-based outcomes, and two-level multilevel modelling approach for keyworker outcomes to estimate the average effect of the treatment allocation using a Huber-White (HW) robust error procedure to account for heteroscedasticity. We anticipate including fixed effects for delivery site and time from randomisation (to account for ongoing referral throughout the pilot). We will also adjust for stratification factors used at randomisation and report ICCs for clustering. The coefficient will be an estimate of the size and direction of the treatment effect and its significance will be tested with a two-tailed 5% Type I error threshold.

The analysis explore the influence of trial arm allocation compliance using Complier Average Causal Effect Analysis, by including intervention receipt in an instrumental variable analysis. The analysis will also include an exploratory analysis with sub-groups or other exploratory analysis including analysis of harms.

All analysis will adhere to good spreadsheet design principles and document the sequence of steps used to get from raw data to findings to enable review. All data cleaning and analysis will be undertaken in R statistical software. All code and analysis will be quality assured by a second member of staff and includes both the logic and the arithmetic of analysis. Full records of code will be shared with the DfE and published to enable replication.

Implementation and process evaluation

The aim of the Implementation and process evaluation (IPE) will be to address key questions of implementation and delivery including fidelity, dosage and quality, reach and responsiveness, acceptability as well as mechanisms of change, barriers and enablers to implementation and capacity and capability to implement.

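### Huber-White errors with a two-sided 5% test on 10 randomised local authorities (6 v 4), with no small-sample correction named, reject a true null too often in their usual form

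*Protocol*

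**What the plan says.** In the Randomisation and blinding section, "The unit of randomisation is at the local authority level". The opening summary says that "The pilot RCT therefore comprises ten local authorities, six in the intervention group and four in the control group".

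The Analysis section of the impact evaluation expects three-level models for family outcomes and two-level models for keyworker outcomes, "to estimate the average effect of the treatment allocation using a Huber-White (HW) robust error procedure to account for heteroscedasticity". It adds "We will also adjust for stratification factors used at randomisation"; Table 1 gives LA structure as the stratification variable. For the treatment coefficient, "its significance will be tested with a two-tailed 5% Type I error threshold".

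The section names no small-sample variance correction, reference distribution or degrees of freedom. It is worded as what the team anticipates, and it says a later statistical analysis plan (SAP) will set out the strategy in full.

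**The concern.** The Huber-White (sandwich) variance is justified when there are many independent clusters. Here the independent units are ten LAs, split unequally, and the LA-structure terms use up several of the few LA-level degrees of freedom. Residuals from a model fitted to ten points are too small on average, so the sandwich understates the LA-level variance. A normal reference then ignores how poorly that variance is estimated.

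At stake are the width of the confidence intervals and how readily a chance difference between LAs is called significant. The first aim of the pilot is indicative evidence of impact, and the feasibility section asks whether the model shows enough promise for a full trial. Intervals that are too narrow would misinform that judgement. The approach is anticipated for all variables, so the point is not confined to the primary outcome.

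**Working it through.** **1. The protocol's own figure.** Inputs from Table 2: K = 10 LAs, J = 56 families per LA, n = 1.5 individuals per family, ICC 0.1 (LA) and 0.3 (family), pre/post value 0.6 at every level, power 0.8, two-sided 5%. Families: "Intervention: 361 Control: 199 Total: 560", so P = 361/560 = 0.645 by families, or P = 6/10 = 0.6 by LAs.

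MDES = M × √{(1 − R²)[0.1/K + 0.3/(KJ) + 0.6/(KJn)] / [P(1 − P)]}, where M is the sum of the 97.5% and 80% critical values.

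- The bracket is 0.1/10 + 0.3/560 + 0.6/840 = 0.01125. With 0.6 used as R², 0.4 × 0.01125 = 0.0045.
- P = 0.6: √(0.0045/0.24) = 0.1369. With t on 7 df, M = 3.261 and MDES = **0.446**.
- P = 0.645: √(0.0045/0.2291) = 0.1402. With t on 8 df, M = 3.195 and MDES = **0.448**.
- Normal values, M = 2.802: MDES = 0.384 (P = 0.6) to 0.393 (P = 0.645).
- If 0.6 is read as a correlation, as it is labelled (R² = 0.36), normal values give 0.485-0.497 and t on 8 df gives 0.553-0.566. Neither is 0.446.

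So 0.446 is matched only with 0.6 as R² and t values on 7-8 df.

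**2. How far the sandwich falls short, without structure terms.** For a difference of LA means with equal variance σ², the true variance is σ²(1/6 + 1/4) = 0.417σ². The uncorrected sandwich has expectation σ²(5/36 + 3/16) = 0.326σ². The ratio is 0.78, so the standard error is about 12% too small (√0.78 = 0.885) before any question of the reference distribution.

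**3. False-positive rate under the null.** LA means were simulated with 6 v 4 LAs, the treatment coefficient was estimated by least squares, and the test was at nominal two-sided 5%. For the structure-adjusted runs, the allocation rules in Randomisation and blinding imply 2 county, 2 metropolitan and 3 London authorities, and 12 − 7 = 5 unitary authorities. Which two control LAs left is described by reason, not by type, so all 15 distinct patterns consistent with those rules were run.

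| Procedure | No structure terms | Four-category structure adjusted |
|---|---|---|
| Uncorrected sandwich, normal reference | about 12% | about 19-31% |
| Sandwich × G/(G-1), t on 9 df | about 7% | about 13-24% |
| Sandwich × K/(K-p), t on K-p df | about 5.5% | about 4-11% |
| Model-based standard error, t on K-p df | about 5% | about 5% |
| CR2 with Satterthwaite df | 4.7-4.8% | 4.4-4.6% (one pattern) |

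Here G = K = 10 and p is the number of LA-level coefficients: K-p is 8 without structure terms and 5 with three. The Satterthwaite df for CR2 are about 6.5 and about 3.4 respectively.

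**4. Does the multilevel model cure it?** With unequal LA sizes and an LA variance estimated by REML, Huber-White errors at LA level with a normal reference still reject 12-13% of the time (LA ICC 0.05 and 0.1). The model-based standard error from the same fit rejects 8-9% with a normal reference and 4.9-5.9% with t on 8 df. A random LA intercept alone is therefore not enough; the standard error and its degrees of freedom matter.

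**The case against.** The strongest reply is that the decisive details are left to the SAP, which is normal, and that the text only anticipates a method. The size of the problem also depends on implementation: K/(K-p) scaling with t on K-p df gives about 5.5% without structure terms. The stated MDES already matches t values on few degrees of freedom, so the team may well intend a t reference. All of this stands as a limit. A reader might infer that the trial's p-values and intervals will be wrong; the document does not support that, because a SAP that adds a suitable correction would remove most or all of the excess. What remains is that the protocol positively chooses an estimator unsuited to ten clusters and pairs it with a 5% test. A SAP that follows that wording with common defaults inherits the fault.

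Other limits also stand:

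- The rates are for continuous outcomes. The two closure outcomes are yes/no and were not simulated, nor was a separate keyworker model.
- The anticipated terms for delivery site and time from randomisation were not included.
- A model-based t-test assumes equal LA-level variance. If control LAs had 1.5 or 2 times the standard deviation of intervention LAs, the pooled t-test on 8 df would reject 7.3% or 9.1% of the time. Wanting some robustness is therefore reasonable.
- The trial is a pilot, and no progression criterion in Table 13 turns on a p-value. That lowers the consequence but does not make the intervals right.

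Because allocation was restricted ("The remaining Unitary authorities were allocated randomly across trial arms", the rest largely by rule), a reader might also infer a floor on any randomisation p-value. No randomisation test is planned, so that does not bear on this point.

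**Conclusion.** The point holds conditionally. Applied in its usual form to ten LAs, the planned procedure has a false-positive rate for continuous outcomes of about 12% (uncorrected, normal reference) or 7% (G/(G-1), t on 9 df). With LA structure adjusted as planned, these become about 19-31% or 13-24%. The figures assume equal LA-level variances, inference at LA level, and an LA mix of 2 county, 2 metropolitan, 3 London and 5 unitary authorities before drop-out. The ranges reflect the unstated types of the two lost controls. The power calculation appears to allow for few clusters; the analysis text does not, and the two should agree. The 20-31% end should not be read as the expected error rate of this trial: it applies only if no correction is made.

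**What to change.** Keep the planned multilevel model with LA as a level, and state in the protocol or SAP, before analysis, that inference on the treatment effect uses LA-level degrees of freedom:

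- **Continuous outcomes:** REML with Kenward-Roger or Satterthwaite df. If robustness to unequal variances is wanted, use a CR2 sandwich with Satterthwaite df in place of the plain Huber-White errors.
- **Yes/no closure outcomes:** a matching small-sample method, such as an LA-level summary analysis with t on K-p df.
- **Reference distribution:** state the df with and without LA-structure terms, and make the power calculation consistent with them.

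The work is SAP wording and standard R packages; R is already the planned software. The statistical cost is wider intervals. The critical value rises from 1.96 to 2.31 on 8 df (2.31/1.96 = 1.18, so 18%) or to 2.57 on 5 df with three structure terms (2.57/1.96 = 1.31, so 31%), before any correction of the standard error itself. CR2 with structure terms costs more, because its df are about 3.4. On 5 df, and keeping 0.6 as R², the MDES becomes 3.490 × 0.1369 = 0.478 to 3.490 × 0.1402 = 0.489.

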As is typical of trials in the field of social policy, the trial is unblinded. Keyworkers and families will know they are part of a pilot study. Keyworkers will be notified when undertaking training as part of the pilot. Families will be told when they are asked to consent to taking part in the pilot study. This lack of blinding is a necessity of the trial design. However, we have selected standardised self-reported outcomes and routinely collected early help data for family outcomes to avoid observer bias that may be introduced if outcomes were to be assessed by unblinded keyworkers for example.

In early discussions, local authority structure, size of Free School Meals population, and rate of Children in Need were identified as some of the possible variables that could be used to stratify and randomise the local authorities signing up to the Supporting Families trial. All three of these alternatives were examined to establish what approach might work best to provide an equitable distribution of families and key workers supporting across the two trial arms. Based on this randomisation will be stratified by local authority structure.

The randomisation procedure by LA structure was be carried out using a combination of random allocation rules to ensure equal arm allocation (control = 0, intervention = 1). The random allocation rules were generated in the statistical package R for each local authority and were combined in Excel to carry out the randomisation. To make the distribution more equitable, a special allocation procedure was used for local authority

⁵² Burridge, H., Nolan, J., & Stanford, M. (2023) Piloting the implementation of systemic training and feedback tools in Rotherham's Early Help & Family Engagement Service: Evaluation report. <https://www.eif.org.uk/files/pdf/piloting-implementation-systemic-training-feedback-tools-rotherham-early-help-family-engagement.pdf>

structures with uneven numbers, utilising the number of families supported as set out in local authority expressions of interest for the pilot. This included:

- Randomly allocate County Councils to each trial arm.

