- Sex of the parent/carers
- Ethnicity of the child
- Ethnicity of the parent/carers
- Whether the child has a Special Educational Needs (a SEN statement or Education Health and Care Plan)
- Whether the parent/carers have a disability
- The work status of the parent/carers
- Whether the child has English is an Additional Language
- Whether the parent/carers has English is an Additional Language
- The work status of the parent/carers
- Whether the child is eligible for Free School Meals.

Assessment data will also include information collected as part of DfE's early help dataset:

- Family ID
- Date assessment started
- Whether the case is a re-referral
- Whether the case is eligible for the Supporting Families Programme
- Family Need identified from items with the Supporting Families Outcome Framework⁹⁰

Closure data will include information collected as part of DfE's early help dataset:

- Family ID
- Reasons for closure
- Outcome at closure using items with the Supporting Families Outcome Framework⁹¹

Keyworker outcome measures

Data for the final two outcome measure (changes in professional wellbeing and changes in systemic practice) will be collected from all keyworkers in the study local authorities via an online survey emailed to them at the start of the trial and at the end of the study.

⁹⁰

https://assets.publishing.service.gov.uk/media/62471c2be90e075f08be4248/Annex_A_National_Supporting_Families_Outcome_Framework.pdf

⁹¹

https://assets.publishing.service.gov.uk/media/62471c2be90e075f08be4248/Annex_A_National_Supporting_Families_Outcome_Framework.pdf

Keyworkers in the intervention group will also be asked questions on these measures in a post-training survey.

Compliance and fidelity

Steps will be taken to monitor compliance and identify risks to contamination. The local authority level randomisation design has the advantage of making risks to contamination low as the model to embed systemic practice will only be implemented in intervention local authorities. In addition, local authorities in the trial are not geographical neighbours, meaning it is unlikely that families will move from one to another.

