| Poor understanding of the practice model which is not informed by evidence, practice or lived experience | Delivery | Low / High | 
The delivery and evaluation team have extensive knowledge of the practice model. In addition to the previous work undertaken. A comprehensive co-design period with an expert working group to produce detailed practice model and use journey maps which include key elements of the intervention.
 |

| Risk | Risk category | Likelihood/Impact | Mitigation strategy |
|---|-----------------------|-------------------|---|
| Limited understanding of local authority needs and context | Delivery | Medium / High | Work closely with local authorities in the co-design stage to collect contextual information and use initial IPE fieldwork to collect this information. |
| Low recruitment and/or retention and/or low participation rates keyworkers | Delivery | Medium / High | 
Ensure training and the model is focused on the needs of keyworkers and contextualised. Comprehensive co-design period with expert working group.
 
Rapidly feed in findings from early stage IPE on identified barriers and possible solutions to delivery of training and embedding the model etc.
 |
| Low fidelity and consistency in delivery across local authorities | Delivery | Medium / High | Develop a standardised systemic practice model in the co-design stage with expert working group. Explore inconsistencies in the IPE rapidly feedback to IFT and local authorities. Evaluation design will spread fieldwork effort across sites to enable variation to be explored and a fidelity checklist will be developed. |
| Temporary or permanent loss of IFT & Coram delivery team | Delivery & Evaluation | Medium / Low | The full team would be kept up-to-date through internal catch ups so would be able to 'pick up' tasks at any stage; good record keeping; ability to draw on extensive capacity at IFT to draw on qualified trainers and teachers. |
| Specific areas of work demand more time / resource than expected. | Delivery & Evaluation | Medium / Low | Careful project/budget management and open/close communication between key partners. We have robust project management processes with monthly completion of timesheets, monthly project planning to review days on project budgets, weekly staff meetings to identify priorities for the week and regular communications around project |

| Risk | Risk category | Likelihood/Impact | Mitigation strategy |

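### Fixed effects for delivery site span an arm allocated by whole local authority, so the anticipated model does not identify the treatment effect

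*Protocol*

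**What the plan says.** The protocol's Randomisation and blinding section states that "The unit of randomisation is at the local authority level". The opening summary gives the numbers after two control LAs withdrew: "The pilot RCT therefore comprises ten local authorities, six in the intervention group and four in the control group". Allocation used LA type: "Based on this randomisation will be stratified by local authority structure".

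The Analysis section of the impact evaluation plans a three-level model for family outcomes and a two-level model for keyworker outcomes, with Huber-White standard errors. For that model it says "We anticipate including fixed effects for delivery site and time from randomisation". The next sentences add "We will also adjust for stratification factors used at randomisation and report ICCs for clustering" and "The coefficient will be an estimate of the size and direction of the treatment effect".

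The protocol does not define delivery site. Two places bear on its meaning. Compliance and fidelity says that "the model to embed systemic practice will only be implemented in intervention local authorities". Table 14, in the row on consistency of delivery across LAs, says "Evaluation design will spread fieldwork effort across sites to enable variation to be explored", where sites appears to mean the LAs.

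The sample size section (Table 2 and Figure 4) treats the LA as a clustering level with an intraclass correlation of 0.1.

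**The concern.** When whole clusters are randomised, the arm effect is a comparison between clusters. Fixed effects for the clusters, or for units nested inside them, use up all between-cluster information and leave none for arm. The clause therefore defeats the purpose of the model it belongs to.

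The protocol applies this modelling approach to all outcomes, so the primary goal-based outcome and the family and keyworker secondary outcomes are all affected. Providing indicative evidence of impact is one of the pilot's two primary aims.

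If site means the LA, the clause also conflicts with its surroundings. LA structure is constant within an LA, so LA fixed effects absorb that adjustment. They also absorb the LA-level variance from which an LA intraclass correlation would be reported. The power calculation rests on a different model, one with the LA as a clustering level.

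**Working it through.** **Plan's own figure.** Inputs from Table 2 and Figure 4: K = 10 LAs, J = 56 families per LA, n = 1.5 individuals per family, ρ3 = 0.1 (LA), ρ2 = 0.3 (family), two-sided alpha 0.05, power 0.8. P = 6/10 = 0.6 is the share of LAs in the intervention arm. For a three-level design with treatment at LA level:

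Var = (1 − R²) × [ρ3/K + ρ2/(KJ) + (1 − ρ2 − ρ3)/(KJn)] / [P(1 − P)]

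MDES = [t(0.975, df) + t(0.80, df)] × √Var

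With R² = 0.6 and df = 10 − 2 − 1 = 7, MDES = 0.4465, against the stated 0.446. The figure therefore reproduces under a model with the LA as a random level. It needs the tabulated 0.6 to be used as R². Read as a correlation (R² = 0.36), the same formula gives 0.565. That is a separate matter and does not affect what follows.

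**Identification, site = LA.** Let D1 to D6 be the indicators of the intervention LAs and D7 to D10 those of the control LAs. Then arm = D1 + … + D6 for every observation.

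| Fixed-effects design | Columns | Rank |
|---|---|---|
| Intercept + 9 LA dummies + arm | 11 | 10 |
| The same + time from randomisation | 12 | 11 |
| Intercept + arm + time + 29 team dummies (illustrative: 3 teams per LA) | 32 | 31 |
| Intercept + arm + time, no site terms | 3 | 3 |
| The same + 3 LA-structure dummies (illustrative spread of structures over arms) | 6 | 6 |

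Regressing arm on the LA dummies leaves a residual sum of squares of zero to machine precision. The time term does not repair the deficiency, and neither does a finer meaning of site. Removing the site terms does. Huber-White errors change the variance estimate, not identification.

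**What software would show.** If site is entered before arm, the arm column is the redundant one and no treatment coefficient appears. If arm is entered first, a site dummy is dropped and the coefficient labelled arm is the difference between two reference sites. In one simulated data set with site = LA, that coefficient was −0.128, exactly the difference between the two reference LAs, while the difference in arm means was 0.350.

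**Fallback contrast.** An analyst could average the six intervention LA effects and subtract the average of the four control LA effects. That is computable, but its standard error treats the LAs as fixed. The bracket in the variance formula shows what is lost:

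- LA: 0.1/10 = 0.01000
- Family: 0.3/560 = 0.00054
- Individual: 0.6/840 = 0.00071
- Sum: 0.01125; LA share = 0.01000/0.01125 = 89%

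The factors (1 − R²) and P(1 − P) cancel, so the share is the same for R² = 0.36 and 0.6. At R² = 0.36 the variance is 0.0300, of which 0.0267 is at LA level. The standard error would be √0.00333 = 0.058 instead of √0.0300 = 0.173, one third of its proper size. Under the null, a nominal 5% normal test would reject when |Z| > 1.96/3 = 0.653, about 51% of the time.

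**The case against.** The wording is provisional, and the protocol promises a final SAP before any analysis. This stands as mitigation, since the error can still be corrected in time. It does not remove the point: the clause names a term that cannot coexist with the stated target, which is different from leaving a detail to the SAP.

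Delivery site is undefined, so its nesting within one LA is an inference. That is also fair. But the protocol describes no delivery unit spanning both arms, and it confines delivery to intervention LAs.

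A reader might infer that the trial cannot estimate its treatment effect, or that its results are bound to be uninterpretable. The protocol does not support that. The same paragraph, with the power calculation, contains a workable model, and one clause contradicts it. Nor is it certain that a single-LA contrast would be reported as the effect. That depends on term order and on what site means. A missing arm term would be conspicuous, and a second member of staff is to check the logic of the code. The 89% matters only if the fallback contrast is used.

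The analyst may well notice. The repair would then be chosen with the data in hand, whereas the protocol relies on an a priori analysis plan to prevent bias.

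**Conclusion.** The point holds as an internally contradictory specification. As written, the arm coefficient is not identified (11 columns, rank 10 with ten LAs), for the primary outcome and for every family or keyworker outcome modelled this way. This rests on each site lying wholly within one LA, which is inferred from the protocol because the term is undefined. The rank result needs no numerical assumption. The 89% share and the threefold understatement of the standard error rest on the plan's intraclass correlations and equal cluster sizes, and describe only the fallback contrast. The randomised comparison itself remains estimable once the clause is removed. Because the clause concerns the headline estimate, it should be corrected before analysis even though the correction is small.

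**What to change.** Delete delivery site from the fixed effects and keep the rest of the planned model:

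- arm as a fixed effect;
- LA as the random level (level 3 for family outcomes, level 2 for keyworker outcomes);
- LA structure and time from randomisation as already planned;
- the baseline score where one is collected (the two closure outcomes have none).

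If team or locality effects are wanted, enter them as random effects nested within LA. If delivery site was meant as something that crosses arms, the protocol must define it. Make the change in the protocol and SAP before any analysis. It costs one line of wording and needs no extra data or sample.
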